8.3 Test of Cure (TOC) Post Treatment Visit

Day 11 – 14 (one – four days after completing the study product)

Subjects will return for a follow-up visit two – four days after completing the study product. At this follow-up visit, a Study Nurse/Nurse Practitioner/Physician will perform assessments of the subjects. Using a standardized interview form (symptom questionnaire), the subjects and/or their parent(s) or legal guardians will be asked to provide a subjective evaluation of the presence or absence of UTI symptoms and possible side effects of the antibiotic like diarrhea or a rash. Parent(s) or legal guardian(s) will also be asked to report any inter-current illnesses (e.g., upper respiratory infection, pharyngitis, otitis media, sinusitis), the name and duration of concomitant therapy, and potential side effects of study product. They will also be asked if the subject sought medical care for possible recurrence of UTI, the records of the encounter including microbiology culture results will be obtained so the SCOUT Study physician,

nurse practitioner or nurse can follow up with the child’s parent(s)/legal guardian(s) and PCP. The Study Nurse/Nurse Practitioner/Physician will collect a second stool sample, the medication diary and the study product bottle. Subjects at CHOP who agree to the Microbiome sub-study will have additional peri-rectal, anal, and stool swabs collected, if applicable. The subject’s temperature will also be taken and the child will be assessed for any suprapubic, abdominal, or flank pain or tenderness. In addition, the Nurse will collect a urine sample for urinalysis and culture from all subjects. The Study Nurse/Nurse Practitioner/Physician will use the bag technique on asymptomatic infants and young children (before they are toilet trained) and the clean catch technique for older toilet trained children. For symptomatic infants and young children a urine sample will be obtained using the clean catch technique (or catheterize if unable to capture with clean catch).

If the subject is symptomatic and the urine culture is positive, the child will be treated outside this protocol by a physician not associated with the SCOUT Study per current standard of care or if they prefer the parent(s)/legal guardian(s) can choose to have their child treated by their PCP/pediatrician (See Table 5 for details on which scenarios require referrals to non-SCOUT physicians at or after the Test of Cure Visit.). Subjects that are asymptomatic with a positive urine culture (specimen collected via bag) will continue with the study as planned. NOTE: Subjects that are diagnosed with a culture positive UTI prior to the TOC Visit (between Day 6 and Day 11-14 TOC Visit) will have the above listed procedures performed during the Interim Visit for reoccurrence of symptoms excluding the stool specimen collection. Data obtained from this visit will apply towards the primary endpoint. They will not have to return for the TOC visit.

Table 5: SCOUT Study Referrals to outside physicians at TOC or later.

Scenario	UTI Symptomology		Urine culture result		Pyuria present		Follow-up required:	Repeat urine culture result/outcome	
	Symp	Asymp ¹	+	-	Yes	NO			
1	X		X		X		Refer to non-SCOUT physician		
2	X		X			X	Refer to non-SCOUT physician		
3	X			X	X		Follow-up required. Contact subject in 24-48 hrs. Perform repeat urine culture if still symptomatic. If asymptomatic, continue with study as planned	+	-
4	X			X		X	Follow-up required. Contact subject in 24-48 hrs - if still symptomatic - perform repeat culture. If asymptomatic, continue with study as planned	+	-
5		X	X		X		Asymptomatic Bacteriuria, continue with study as planned		

6		X	X			X	Asymptomatic Bacteriuria, continue with study as planned		
7		X		X	X		Continue with study as planned		
8		X		X		X	Continue with study as planned		

Also, for asymptomatic subjects if a urine sample cannot be obtained at this visit, another attempt to obtain a urine sample will be made at the Day 24-30 Outcome Assessment Visit.

8.4 Outcome Assessment Visit

Day 24 - 30 (14 – 20 days after completing the study product):

The Study Nurse/Nurse Practitioner/Physician will administer the symptom questionnaire, take the child’s temperature, and collect a third stool sample. Subjects at CHOP who agree to the Microbiome sub-study will have additional peri-rectal, anal, and stool swabs collected, if applicable. In addition, the child will be assessed for any suprapubic, abdominal, or flank pain or tenderness. The purpose of this visit is to assess for recurrent infections (relapse or reinfection).

If applicable, for asymptomatic subjects for whom no urine sample could be obtained at the TOC visit another attempt will be made to obtain a urine sample at this visit. This sample is taken as a safety measure.

If the subject is symptomatic and the urine culture is positive, the child will be treated outside this protocol by a physician not associated with the SCOUT Study per current standard of care or if they prefer the parent(s)/legal guardian(s) can choose to have their child treated by their PCP/pediatrician. If the families prefer to see their PCP or pediatrician, the Study Nurse, Nurse Practitioner, Physician and/or Study Coordinator will help to facilitate the follow up appointment. The Study Coordinator will share all pertinent information related to the study with the physician.

All of the above procedures will be performed for subjects that were categorized as treatment failures or diagnosed as having asymptomatic bacteriuria prior to this visit. These procedures include stool specimen collection.

8.5 Follow-Up Phone Call

Day 38 – 44 (*28-34 days after completing the study product*):

The Study Nurse, Nurse Practitioner, Physician or Study Coordinator will follow up by phone with the subject’s parent(s)/legal guardian(s) to administer the symptom questionnaire. The purpose of this call is safety and to evaluate for the presence or absence of a new urinary tract infection.

Using a standardized interview form (symptom questionnaire), the subjects and/or their parent(s) or legal guardians will be asked to provide a subjective evaluation of the presence or absence of UTI symptoms. Parent(s) or legal guardian(s) will also be asked to report any inter-current illnesses (e.g., upper respiratory infection, pharyngitis, otitis

media, sinusitis), the name and duration of concomitant therapy, and potential side effects of study product. If the subject sought medical care for possible recurrence of UTI, the records of the encounter including microbiology culture results will be obtained so the SCOUT Study physician, nurse practitioner or nurse can follow up with the child’s parent(s)/legal guardian(s) and PCP. Subjects that were categorized as treatment failures prior to this visit will be asked about the presence or absence of UTI symptoms and the follow-up treatment received.

All children that report symptoms associated with UTI during the phone call will have a visit scheduled to collect a urine sample for urinalysis and culture, and will be treated outside this protocol by a physician not associated with the SCOUT Study per current standard of care or if they prefer the parent(s)/legal guardian(s) can choose to have their child treated by their PCP/pediatrician. If the families prefer to see their PCP or pediatrician, the Study Nurse, Nurse Practitioner, Physician and/or Study Coordinator will help to facilitate the follow up appointment if needed. The Study Coordinator will share all pertinent information related to the study with the physician. A SCOUT Study physician, nurse practitioner or nurse will follow up with the PCP/pediatrician on the child’s status.

8.6 Early Termination Visit

Subjects that choose to withdraw or are withdrawn by the PI prior to the Day 11-14 TOC visit will be asked to be evaluated for UTI symptoms and possible side effects of the antibiotic like diarrhea or a rash. Parent(s) or legal guardian(s) will also be asked to report any inter-current illnesses (e.g., upper respiratory infection, pharyngitis, otitis media, sinusitis), the name and duration of concomitant therapy, and potential side effects of study product. They will also be asked if the child sought medical care for a possible recurrence of UTI. However, no urine or stool sample will be obtained. If the subject presents with UTI symptoms at the termination visit, the SCOUT PI will inform their PCP/pediatrician and share all pertinent information related to the study and urge the parent(s)/legal guardian(s) to follow-up with their PCP/pediatrician.

Study staff will request that subjects that choose to withdraw or are withdrawn any time after the TOC visit be contacted for the Day 38-44 follow-up phone call for assessment of adverse events.

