Subjects that are diagnosed with a UTI while on study treatment and prior to the TOC Visit (between Day 6 and Day 11-14 TOC Visit) will be considered treatment failures and do not have to return for the TOC Visit but they will be asked to return for the Day 24-30 Outcome Assessment Visit and receive the Day 38-44 phone call. Similarly, subjects that are diagnosed with a UTI at any time after the TOC Visit through the Day 38-44 call will continue to return for the Outcome Assessment Visit and receive the Day 38-44 follow-up phone call. A stool specimen will still be collected at the Outcome Assessment Visit for these subjects diagnosed with UTIs (either before or after TOC).

Sub-studies

Seattle Children’s Hospital R21

An R21-funded sub-study titled, “Differences in infecting and colonizing Enterobacteriaceae from short-course vs. standard therapy of pediatric UTI” is being performed with collaborators at Seattle Children’s Hospital. This sub-study hypothesizes that both the antibiotic agent and the length of therapy will affect the patients’ indigenous flora and thus affect both the likelihood of recovering *E. coli* and/or *K.*

pneumoniae from stool and the resistance phenotypes of the recovered isolates. The sub-study will utilize PCR- and sequence-based methods to characterize phylogenetic and resistance properties of the recovered isolates.

Carbapenem resistant enterobacteriaceae

For each enrolled research subject, the stool or perirectal swab collected at the Test of Cure visit will also be utilized to perform additional screening for the presence of carbapenem resistant enterobacteriaceae. The results of this additional screening will be used to determine the prevalence of colonization with carbapenem-resistant Enterobacteriaceae (overall and for specific pathogens) in ambulatory children after completion of treatment for UTI.

Microbiome pilot study

For each subject at CHOP who agrees to participate in the Microbiome pilot study, an additional perirectal swab and anal swab will be collected. The additional swabs will be collected at each visit and will be used to determine the composition of the subjects' microbiome. For subjects in diapers, an additional stool swab will also be collected. The accuracy of microbiome analysis resulting from perirectal swabs will be tested via comparison with analysis performed on stool specimens. The anal swab will be used to assess the presence of skin flora contamination in the peri-rectal swabs.

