6.4.3 Reasons for Withdrawal

The SCOUT protocol has been developed to minimize the number of participants lost to follow-up and reduce barriers to participation. The schedule of contacts is designed to facilitate participant retention through regular contact in a short timeframe.

Participation in the SCOUT Study is voluntary. Subjects and their families can decide to discontinue participation at any time for any reason during the study by notifying study staff.

In addition, the Investigators may discontinue participation for any subject at their discretion: if in their professional opinion, the subject’s health, safety, and/or well-being is threatened by continued participation in the study or they may withdraw those subjects that do not comply with the study, or to protect the subject for safety reasons or for administrative reasons. Subjects may also be discontinued from the study at the Investigator’s discretion for lack of adherence to study treatment or visit schedules, AEs, loss to follow-up or a protocol violation.

Symptomatic subjects that develop a positive urine culture during the study period will not be considered withdrawn from the study, they will continue to be seen/contacted for any remaining study visits as part of safety follow-up. These subjects will be treated outside this protocol by a physician not associated with the SCOUT Study per current

standard of care or if they prefer the parent(s)/legal guardian(s) can choose to have their child treated by their PCP/pediatrician.

Subjects that develop a fever or worsening of symptoms after enrollment but prior to initiation of protocol treatment will be withdrawn from the study and considered entry failures. These subjects will be treated outside this protocol by a physician not associated with the SCOUT Study per current standard of care or if they prefer the parent(s)/legal guardian(s) can choose to have their child treated by their PCP/pediatrician.

It will be documented whether or not each subject completes the clinical study. If the Investigator becomes aware of any serious, related adverse events (AEs) after the subject completes or withdraws from the study, it will be recorded in the source documents and on the CRF.

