6.4.4 Handling of Withdrawals

All withdrawals regardless of reason (whether the SCOUT PI or the parent removed the child from the study), will be followed-up by a phone call one week after their withdrawal to determine their status and if any medical follow up care was sought (in which case an MCN form will be completed).

The Study Coordinator will collect data from the treating physician by completing the Medical Care Notification (MCN) Form.

Symptomatic subjects that develop a positive urine culture will not be considered withdrawn from the study. They will continue to be seen/contacted for any remaining study visits as part of safety follow-up. These subjects cannot be re-enrolled into this study. For symptomatic subjects with positive urine culture and pyuria during the Day 6 - 10 period the study product will be discontinued. Symptomatic subjects with positive urine culture will be treated outside this protocol by a physician not associated with the SCOUT Study per current standard of care or if they prefer the parent(s)/legal guardian(s) can choose to have their child treated by their PCP/pediatrician.

Subjects that withdraw or are withdrawn from the study prior to being evaluable for the primary outcome measure will be replaced.

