10 ASSESSMENT OF SAFETY

10.1 Specification of Safety Parameters

Safety will be evaluated by the collection and analysis of data on serious adverse events (SAEs), clinical laboratory tests, pain assessments, and concomitant medications. The investigator is responsible for documenting all SAEs that are observed or reported throughout the study regardless of their relationship to the study products or procedures.

The study products used in this protocol are established generic products labeled for use in the study population for treatment in the indication, UTI. TMP-SMX cefixime, and cephalexin have been used to treat UTIs in children for decades, have established safety records for pediatric use, and have well described side effect profiles. These are the four most commonly prescribed antibiotics at CHOP and PITT for the treatment of UTIs in children.

The subjects will be followed from the Enrollment Visit through the Day 38 – 44 follow-up phone call (four weeks after completing study product therapy). Subjects on the continued antibiotic treatment arm may have a higher likelihood of developing resistant bacteria than subjects on the placebo arm; however, their risk should be no greater than what occurs in standard clinical practice.

For the purposes of this study, adverse events will be collected from the initiation of the study product (Day 6) through the Day 38 - 44 Follow-up Phone Call (four weeks after finishing the study product).

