Safety Analysis: Safety in this study is related to efficacy. Safety will be evaluated by the collection and analysis of data on SAEs, clinical laboratory tests, pain assessments, and concomitant medications. The investigator is responsible for reporting all SAEs that are observed or reported up, regardless of their relationship to study product. Serious adverse events and abnormal laboratory (if available) results will be compared by treatment arm, with statistical tests for differences in proportion of subjects with serious adverse events between study arms.

Missing Data: Several procedures will be used to conduct data analysis when data for either outcomes or covariates are missing. The first step will be to assess the extent and pattern of missing data. If data are missing for only a few cases, then data analysis will be conducted only on study participants with complete data. However, when such a strategy would result in loss of data from a substantial proportion of participants or would lead to biased or inaccurate results, then some form of imputation will be performed. The form of imputation used will depend on the nature of the data that are missing.

Attrition and Loss to Follow-up: It is expected that loss to follow-up will be minimal in this study. Because the study is of short duration, we are hopeful that we will be able to follow virtually all subjects to study completion. However, some study participants may withdraw consent or may not return for the follow-up visits to determine the primary endpoint. Other participants may not have the endpoint determined due to problems with specimens or laboratory processing. We anticipate that these factors may reduce the sample size by as much as 10%. Thus the sample was increased by approximately 11% to offset this sample size reduction. Note that study participants who disrupt or discontinue study treatment will continue with follow-up and have the study endpoints assessed, and will be included in the ITT analysis.

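### Dosed children who withdraw before the test-of-cure visit have no planned Day 38-44 safety call, although the adverse-event window runs to that call

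*Protocol*

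**What the plan says.** Protocol section 10.1 states that "adverse events will be collected from the initiation of the study product (Day 6) through the Day 38 - 44 Follow-up Phone Call". Nothing there exempts children who withdraw.

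The arrangements for withdrawals are in three places:

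- **Section 6.4.4, all withdrawals.** Each child "will be followed-up by a phone call one week after their withdrawal to determine their status" and to learn whether medical care was sought. If it was, data are collected from the treating physician.
- **Section 8.6, before TOC.** These children "will be asked to be evaluated for UTI symptoms and possible side effects of the antibiotic like diarrhea or a rash". Intercurrent illness, other therapy and care sought are also covered. No urine or stool is taken.
- **Section 8.6, after TOC.** Staff request that "subjects that choose to withdraw or are withdrawn any time after the TOC visit be contacted for the Day 38-44 follow-up phone call", so that adverse events can be assessed.

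Section 6.4.3 lets the investigator withdraw a child at his or her "discretion for lack of adherence to study treatment or visit schedules, AEs, loss to follow-up or a protocol violation". After withdrawal it provides for recording serious, related events if the investigator learns of them.

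**The concern.** The late safety call is requested for children who have already reached TOC and not for those who left sooner. No reason is given. Sections 8.6 and 6.4.4 therefore do not deliver, for one group of dosed children, the collection period that section 10.1 sets.

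What is at stake is the capture of new events. A late reaction, a returning infection or a hospital admission after the one-week call would reach the study only by chance, and section 6.4.3 provides only for events that are both serious and related. Section 10.1 asks for all serious events, whatever their relationship to study product. The gap is relevant here because section 12.4 ties safety to efficacy and section 2.3.1 accepts that the short course may carry a higher risk of treatment failure.

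**Working it through.** The plan gives no figure for this gap, so the check compares the contact schedule with the stated window.

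**Inputs**

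- Window (10.1): Day 6 to Day 38 is 38 − 6 = 32 days; Day 6 to Day 44 is 44 − 6 = 38 days.
- Last planned contact for a child who leaves before TOC (6.4.4): day of leaving + 7.
- Days of leaving: 6 (first study dose), 10 (last planned dose) and 13 (the day before the latest TOC day, Day 14).

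**Formula:** days without planned contact = end of window − (day of leaving + 7).

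| Leaves on | Last planned contact | Uncovered, window to Day 38 | Uncovered, window to Day 44 |
|---|---|---|---|
| Day 6 | Day 13 | 38 − 13 = 25 of 32 (78%) | 44 − 13 = 31 of 38 (82%) |
| Day 10 | Day 17 | 38 − 17 = 21 of 32 (66%) | 44 − 17 = 27 of 38 (71%) |
| Day 13 | Day 20 | 38 − 20 = 18 of 32 (56%) | 44 − 20 = 24 of 38 (63%) |

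The range is 18 to 31 days, or 56% to 82% of the window. This is generous to the plan: it treats the one-week call as a full adverse-event contact, although 6.4.4 describes it as a check on status and care sought.

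**Size of the group.** Protocol section 5 plans about 746 enrolled for 672 evaluable. The 10% loss in section 12.4 gives 672 / 0.90 = 746.7, which agrees. The planned loss is 746 − 672 = 74 children (74 / 746 = 9.9%). Section 12.4 attributes it to withdrawn consent, missed visits, and specimen or laboratory problems. Of these, only children who took study product and then withdrew before TOC are affected, so 74 is a ceiling and not an estimate.

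**Who is in the safety tables.** SAP section 4.2.6 runs the safety comparison on the ITT population. SAP section 5.1 defines that population as children who took at least one dose and were either evaluated at TOC or failed before it. A dosed child who leaves before TOC without a failure is therefore generally outside the tables. A possible exception is a child who had an interim visit, which item (d) of the evaluability rule in SAP section 4.2.6 accepts.

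**The case against.** The best reply is that the Protocol already limits the gap, and much of that reply stands.

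- Stopping study product is not withdrawal. Section 12.4 says that "study participants who disrupt or discontinue study treatment will continue with follow-up and have the study endpoints assessed".
- Children diagnosed with a UTI before TOC are not withdrawn. Under the Protocol Summary "they will be asked to return for the Day 24-30 Outcome Assessment Visit and receive the Day 38-44 phone call".
- Events already reported are followed to resolution or stabilisation, even after the child has left (sections 10.3.1 and 10.4).
- The early termination evaluation asks directly about side effects. If the child has symptoms, the primary care provider is told.

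None of these looks for a new event after the one-week call in a child who has left the study.

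Two stronger readings are tempting, and the documents do not support them.

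A reader might infer that these are the children most likely to have left because of harm. Adverse events are a permitted reason for withdrawal, but the documents give no figures on why children leave. Children who merely stop the product or have a confirmed failure stay in follow-up, and an event known at departure is still followed.

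A reader might also infer that unequal observation time biases the adverse-event comparison between arms. Under the SAP's safety population these children are mostly not in the comparison, so their short follow-up does not enter it. The problem in the analysis is omission, and an extra phone call alone would not cure it.

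**Conclusion.** The inconsistency is real but narrow. For a dosed child withdrawn from the study before TOC, the Protocol schedules no active contact after the one-week call, which leaves 18 to 31 days of a 32- to 38-day window uncovered. This assumes departure on Days 6 to 13 and that the one-week call takes place. The gap concerns new or unreported events only.

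The number of children cannot be derived from the documents. A reader might take the 74 planned losses as the number affected, but that figure mixes causes, and families who are lost to follow-up cannot be reached by any call. The primary endpoint is not affected. The change is worth making because it is cheap and brings sections 6.4.4, 8.6 and 10.1 into agreement.

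**What to change.** **Protocol section 8.6.** Replace the restriction to departures after TOC with a rule such as:

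> Staff will ask the family of every child who took one or more doses of study product and then left the study, whether before or after TOC, to take the Day 38-44 call so that adverse events can be assessed.

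Cross-refer to this rule from section 6.4.4 and keep the one-week call. For families who can be reached, the uncovered period falls to zero.

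**SAP sections 4.2.6 and 5.1.** Define a safety population of all children who took at least one dose of study product, and use it for the adverse-event tables in place of Population 1. Without this, events collected from early leavers would generally not be counted. Because some families will decline the late call, report by arm how many dosed children had no Day 38-44 contact.

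**Cost.** Wording changes in both documents, a revised population note in the table shells, and a small number of extra calls with the existing questionnaire. It remains a request, so some families who have left will refuse.
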